7.3 Consent

The researcher will ask the potential participant (and/or their personal legal representative) to read the written information sheet in order to reach their decision about participation. The researcher practitioner will be present to answer any questions they may have. If, for any reason it is not convenient for the potential participant/personal representative to read the written information sheet immediately, the research practitioner will arrange to return to at an agreed time point. Potential participants/personal representatives will always be given as long as necessary, to consider study participation. However it will be made clear to potential participants/ personal representatives that, whilst inclusion must be within a maximum of 72 hours from symptom onset, in order to increase the potential benefit from the new treatment, the trial drug should be administered as early as possible. If they unable to decide on study participation within 72 hours of symptom-onset, they will become ineligible. If the potential participant/their representative decide that they wish to take part in the trial they will be asked to sign a consent form confirming their willingness to participate.

Capacity to consent may be an issue within this patient group. A formal assessment of capacity will be carried out by an appropriately trained member of the research team where appropriate. Where it is not possible to obtain consent from the potential participant due to lack of capacity, we will seek consent from their personal legal representative. If the patient lacks capacity to consent to participation and no personal legal representative exists, the decision to include the potential participant will be made by a senior member of the clinical team who is independent of the research team (professional legal representative).

In the event that a potential participant has the capacity to consent to participation, but is unable to complete and sign the relevant consent form due to physical difficulties resulting from their clinical condition or pre-existing physical impairments (e.g. visual difficulties or limb weaknesses), witnessed, verbal consent will be obtained. The potential participant will be asked to orally confirm their willingness to participate in each stage of the trial to the professional legal representative (most likely a member of the clinical team independent of the research group) who will then be asked to confirm this consent in writing. In the event that the physical difficulties resolve during the participant's inclusion in the trial, a further consent form will be completed.

Where consent is obtained from the participant's personal legal representative or the professional legal representative in the first instance, the capacity of the participant to consent for themselves will be reassessed before each research assessment/intervention. If the participant regains capacity, they will be given information about the trial and asked to confirm willingness to continue trial participation. Where consent is given by the participant in the first instance, it will be made clear that they will remain in the trial should capacity be lost unless the decision to withdraw them is made by their representative, the research team, or by their clinical team.

Patients entered into the trial will be randomised and assigned a unique trial participant code, which will be used to identify subsequent samples, for communications and for data collection purposes.

Consent to trial participation will include sharing of personal contact data with the trial centre in order to conduct follow-up assessment and the optional consent to storage of blood samples for use in other ethically-approved research.

7.4 Randomisation

Following consent by the patient or their legal representative and the baseline assessment (including baseline blood sample), the patient will be immediately randomised using an independent, bespoke, online randomisation service to ensure third-party concealment of allocation. This randomisation service will be provided by Glasgow Clinical Trials Unit who will design, programme and maintain the online service for the duration of study. 1:1 randomisation will be stratified by site (because of the potential for differences in surgical and post -operative practices), grade of SAH using WFNS (Grades 1&2 vs 3 to 5) and known aneurysmal status (aneurysm confirmed vs aneurysmal status unknown).

Randomisation takes place on Day 0. The first IMP administration should be given as soon as possible after randomisation and within 72 h of ictus. IMP administration will then continue according to the schedule in section 8.4 for a maximum 21 days from ictus or until discharge from neurosurgical care (whichever is earlier). The following diagram illustrates the day of randomisation in relation to IMP administration and data collection.

Day 0	Day 1	Day 2	Day 3	Day 4	Day 5	Day 6	e.t.c
Randomisation			Day 3-5 B	lood sample collection			
Begin IMP administration	Contin	ue IMP/plac	cebo admini	stration for	a maximum	21 days fror	n ictus

7.4.1 Method for participant randomisation and the implementing the allocation sequence

The randomisation system will be set up to allow storage of study drug kits in out-of-pharmacy fridges in each recruiting centre (see below for full details of contain of each study drug kit). A small supply of "unallocated" kits will be stored in these fridges to allow recruitment outside of standard working hours. The randomisation system will ensure participants are only randomised to kits in this fridge at the time of randomisation.

Research staff undertaking randomisation will access the online system using their own unique log-in details following participant consent and collection of baseline blood sample. Details of the recruiting centre code, WFNS grade, date and time (if not known a close approximation should be entered) of ictus and aneurysmal status will be entered onto the system. The system will request confirmation of eligibility before allowing randomisation to be performed. The researcher will be again asked to confirm their password before the randomisation process is complete. Following randomisation, a confirmatory email will be sent to all staff at the recruiting site and to the coordinating centre detailing kit number, participant ID and date and time of randomisation. A printed copy of the randomisation confirmation email will be stored in the Investigator Site File (ISF).

7.4.2 Management of kits at site

The randomisation system will also allow management of kits at the recruiting site. In order to minimise wastage of kits at recruiting sites and to facilitate continued inclusion of participants recruited who move between recruiting sites, an agreed procedure will be followed, which will be detailed in the pharmacy manual.

7.5 Blinding

Blinding will be maintained by use of identically packaged and labelled placebo so that participants (the patient, their personal legal representatives) and all trial staff (including the research team and outcome assessors, but excluding the laboratory staff and the statistician preparing reports for the IDMC) are unaware of treatment allocation throughout the period of the trial.

7.6 Unblinding

Details of the emergency unblinding procedure will be detailed in the Pharmacy Manual and will be available at all times in the Pharmacy Departments at each recruiting site and in the investigator site file.

If the investigator feels unblinding may be necessary then the participant's study drug should be stopped immediately. In the event an unblinding is required, the responsibility at the local sites resides with the PI. When possible the PI should only make the decision to unblind after consultation/discussion with the CI. If the person requiring the unblinding is not the CI/PI then the attending clinician will follow local procedure to unblind. This would be: where possible the treating clinician should request to unblind with the local PI. Where it is not possible to contact the PI/CI for whatever reason, a back-up unblinding procedure will be held in the local Pharmacy sites with specific instructions to follow.

If a decision is made to unblind, the allocation details will be obtained from the online randomisation site using an unblinding login account. This procedure will make sure the safety of the participant is not compromised and that the participants and research staff are not unblinded unnecessarily. Pharmacy might have a second attempt to contact the CI. This will also apply for out of hours.

On receipt of the treatment allocation details the CI/PI will continue to deal with the patient's medical emergency as appropriate.

The study code will only be broken for valid medical or safety reasons e.g. in the case of a severe adverse event where it is necessary for the investigator or treating health care professional to know which treatment the patient is receiving before the participant can be treated. Subject always to clinical need, where possible, members of the research team will remain blinded.

The CI/PI will document the breaking of the code and the reasons for doing so on the CRF/data collection tool, in the site file and medical notes. It will also be documented at the end of the study in any final study report and/or statistical report. The CI/Investigating team will notify the Manchester CTU in writing as soon as possible following the code break detailing the necessity of the code break. The Manchester CTU will then notify the Sponsor and the relevant authorities as required. The decision to code break will be included on the Development Safety Update Report (DSUR). The written information will be disseminated to the Independent Data Safety Monitoring Committee (IDMC) for review in accordance with the IDMC Charter.

As part of the terms of the Investigator Sponsored Study (ISS) agreement, Swedish Orphan Biovitrum (Sobi) will also be informed of the decision to code break.

As the investigator is responsible for the medical care of the individual trial subject (Declaration of Helsinki 3§ and ICH 4.3) the coding system in this blinded trial includes a mechanism that permits rapid un-blinding (ICH GCP 5.13.4). While discussion with the PI/CI should be sought, the investigator will not be required to discuss un-blinding if he or she feels that emergent unblinding is necessary.

7.7 Trial Assessments

7.7.1 Pre-randomisation evaluation

At screening, research staff will review patient health records to confirm eligibility according to the eligibility criteria in section 6. This will include basic demographics (age), past clinical history and radiological data. No identifiable participant data will be recorded. An anonymised screening log will be maintained. Following consent, participants will undergo a baseline assessment which will include transcription of source data including baseline research blood sampling, demographics (date of birth, sex, treating centre), and past clinical & medical history (date and time of ictus; World Federation of Neurological Societies (WFNS) grade at first presentation; pre-morbid mRS; pre-morbid risk factors (including smoking, hypertension, diabetes, ischaemic heart disease); existence of pre-morbid anxiety, depression or fatigue). A 10ml baseline blood sample will be taken immediately following consent and before randomisation for measurement of plasma IL-6. Sampling will be undertaken to ensure the minimal inconvenience to the patient and wherever possible blood will be sampled from an established central venous or arterial line. Where possible, research bloods will be taken at the same time as clinical bloods. Clinical reports of renal function and full blood count will be checked by an appropriate member of the PI team prior to randomisation (see exclusion criteria). Additional tests of full blood count, renal function, and liver function will be performed at the discretion of the clinical team as part of the direct clinical care and will be reviewed at the pre-specified post-randomisation evaluations as detailed below.

7.7.2 Post-randomisation evaluations

Adverse event (AE) reporting checks will be made by a delegated member of the research team at the day 3-5 assessment, between day 10-12, on the final day of study treatment and at day 30 post randomisation. Patients enrolled into the study will also be under continuous clinical observation as part of their routine direct clinical care. The site PI or delegate will liaise with the clinical team on a daily basis and a telephone number will be provided as a direct point of contact with the research team for discussion of any concerns relating to the study or administration of the study drug. Any adverse events noted outside the prespecified reporting checks will be processed.

Details of each administration of study drug will be recorded in the case report form (CRF) and the clinical drug administration record. This will include details of administration site, date and time of administration.

A second research blood sample will be taken at 3-5 days post randomisation for measurement of plasma inflammatory markers (IL-6) (putative mediator) and IL-1Ra concentration (treatment fidelity and validation of randomisation). Further clinical data (survival check; detail of target aneurysm, including confirmation, position and treatment) will be collected at the day 3-5 post randomisation assessment.

On the final day of study treatment another survival check will be performed. As part of the end of treatment assessment the participants will be asked to confirm their willingness to be contacted at 30 days and 6 months of the date of randomisation and contact details of the participants (or next of kin) will be confirmed.

A final AE check and survival check will be performed at 30 days post randomisation on all patients who have received at least one dose of study drug and will be completed by local research staff. To avoid

distress to the next of kin, the survival check will be performed by contacting the participant's general practitioner. Patients who have been discharged to their own home will be contacted directly by telephone. If the patient is unable to provide this information it will be obtained from the patient representative. In cases where a patient has been transferred to another in-patient care setting, e.g. rehabilitation centre or local district hospital, this information will be sought from the local healthcare provider (usually local treating physician or nursing staff). This final AE check will be completed for all participants, including those with non-aSAH who received a small amount of study drug prior to withdrawal. Full details of AE collection procedure can be found in section 9.1.1. The patient's own general practitioner (GP) will be informed of study participation by letter (including a copy of the participant information sheet and informed consent form) upon discharge from the treating centre sent by a delegated member of the research team.

As part of the assessment at 30 days post randomisation research staff should also ensure details of rebleed, cerebrospinal fluid (CSF) diversion, delayed cerebral ischaemia (DCI) and CSF infection have been completed in the CRF. DCI is defined as the occurrence of focal neurological impairment or decrease in the Glasgow Coma Scale (GCS) by at least 2 points as long as this was not apparent immediately after aneurysm occlusion, and that the deficit could not be attributed to other causes such as hydrocephalus or electrolyte disturbance. CSF infection is defined as definite if it's microbiologically proven or probable if clinical signs and symptoms of CSF sepsis leads to a clinician starting anti-microbial treatment. Length of stay within the neurosurgical service should also be recorded through recording of discharge date from neurosurgical service and discharge destination (or continued status as neurosurgical service patient).

The final outcome assessment will be performed at 6 months (+/- 28 days) from randomisation and will record mortality and primary and secondary outcomes. This will be coordinated centrally. A survival check will be performed by contacting the participant's general practitioner to avoid any distress to next of kin. The assessment will be performed by telephone where possible. This is our first preference for data collection and has influenced our choice of measures. However, if people need more support we can offer a face-to-face interview at any routinely scheduled out-patient appointment in which to complete the outcome assessments. Furthermore, if the participant is unable to answer the questionnaires due to problems with capacity, or ongoing problems with communication or cognition, the researcher may ask a relative or friend, general practitioner or another healthcare provider to assist the patient in completing the questionnaire.

These options will be outlined on the information for participants, personal legal representative and professional legal representative sheets provided as part of the consent process.

The final outcome assessment will record mRS which includes mortality and in survivors, additional outcome assessments relating to anxiety, depression (Hospital Anxiety and Depression scale; HADS), fatigue (Greater Manchester Stroke Assessment Tool; GM-SAT fatigue question)³⁸ and Fatigue Severity Score⁴¹ and quality of life (EQ-5D-5L). Where the final assessment is performed by the coordinating centre, a standard letter will be sent to the recruiting PI informing him/her of the modified Rankin Score.

7.8 Withdrawal Criteria

Participants without confirmation of aneurysm within 72 hours of randomisation and those patients found to be non-aneurysmal post randomisation will be withdrawn from treatment. If participants are withdrawn for this reason they will continue to be followed up until their safety (30 days post randomisation) assessment. While baseline plasma samples collected from these participants will not be analysed for this trial, the samples will be shipped to the trial centre (see section 7.9) for potential use in future research (provided consent was given for this). If consent was not given for use of samples in future research, the sample must be destroyed at the participating site as per local procedure

In the event of death between randomisation and the diagnosis of aneurysm (usually by CTA), these participants will be excluded as 'Failed To Confirmed Aneurysm' and this event should be reported as detailed in notification of death (section 9.5).

Participants have the right to withdraw from the trial treatment or trial participation at any time, without having to give a reason and without any effects on their clinical care. The withdrawal process will be explained prior to consent.

If a participant is withdrawn from trial treatment, study drug will be stopped immediately and no further blood samples will be obtained. Subsequent assessments of patient safety and an end of study outcome will be completed as planned. All data and samples will be retained and included in analyses. Trial treatment should be stopped for the circumstances listed below.

- Uncontrolled AE/SAE that is related to, or potentially related to, study drug;
- Participant or personal legal representative decision, or at the PI discretion;
- If a severe allergic reaction occurs administration of IL-1Ra should be discontinued and appropriate treatment initiated;
- If participants become neutropenic (ANC <1.5 x 10⁹/l), IL-1Ra treatment should be discontinued;
- Pregnancy;
- Symptomatic deterioration where the investigator feels the participant's receipt of study drug is no longer clinically appropriate;
- Study suspended or stopped for any reason.

Subarachnoid haemorrhage patients may suffer uncontrolled AEs or SAEs due to the nature of the condition. Therefore only uncontrolled AEs or SAEs that are related to, or potentially related to, study drug should be a direct reason for withdrawal from trial treatment. If a participant suffers any uncontrolled AE or SAE that is not related to study drug, but that in the investigator's opinion it would be in the participant's best interest to end trial treatment, the participant can be withdrawn from trial treatment based on the penultimate point listed above.

If the participant withdraws from trial participation, no further assessments will be performed. The information required for the final 30 day safety information will be gathered from secondary sources including clinical records. Study data and samples will be retained and included in analyses unless the participant requests it be destroyed. It is the responsibility of the participating site research teams to ensure the participant's wishes are met. Samples stored at the participating site must be destroyed as per local procedure and the central laboratory and Manchester CTU must be notified of the participant's request for their data and samples to be destroyed.

Participants and their representatives do not have to give a reason for their withdrawal. However, where available, the research team will record reason for withdrawal or lack of this in the medical notes and the CRF.

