2.1.2 Justification for inclusion prior to confirmation of aneurysm

The initial clinical and computed tomography (CT) scan diagnosis on arrival in the neurosurgical centre is normally of SAH (not aSAH) because a proportion (around 20%) of patients with confirmed SAH is subsequently found on angiography not to have aneurysm. These non-aneurysmal SAH (non-aSAH) patients usually have mesencephalic bleed which has a much better outcome than aneurysmal bleed. Diagnosis of aneurysm requires an angiogram (usually CT angiogram; CTA) which may not be performed immediately.

Earlier treatment is known to be associated with better outcome in preclinical studies^{34,35} so to avoid delay, we propose to randomise following the diagnosis of SAH which may be prior to confirmation of aneurysm. People subsequently found to be non-aneurysmal (usually angiogram is performed within 48 hours or less of arrival at the neurosurgical centre) will be withdrawn from the trial. We will encourage early approach to allow people as much time as they need to consider participation and so approaching as soon as the initial SAH diagnosis is made seems most logical. Patients for whom aneurysm is not confirmed will not be included in outcome analysis although they will be included in Adverse Event monitoring.

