11.7 Subject Population

We will seek outcomes for all randomised participants with confirmed aSAH regardless of protocol adherence and include them in analyses under the allocated group. That is, the analyses will be by intention to treat for all randomised participants whose confirmed diagnosis is aSAH. The anticipated 20% of randomised patients who are confirmed with alternative diagnoses will be excluded from all efficacy and mechanism analyses. This post-randomisation exclusion will not cause statistical bias because neither the treatment itself nor knowledge of the allocation (achieved by concealment and blinding) can affect the diagnosis. Patients excluded post-randomisation due to absence of confirmed aSAH will be analysed separately for adverse events.

Given the study population it is anticipated that all participants will receive at least one dose of their allocated study drug. It will be reported if an SAE occurred in a participant who did not receive their allocated study drug and an additional, separate "treatment received" population will be defined in this instance.

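### Section 7.8 ends follow-up at day 30 for participants not confirmed within 72 hours, while Section 11.7 seeks the 6-month outcome for every confirmed aSAH participant, so late-confirmed cases fall under conflicting rules

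*Protocol*

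**What the plan says.** Section 7.8 of the protocol sets one trigger with two limbs: "Participants without confirmation of aneurysm within 72 hours of randomisation and those patients found to be non-aneurysmal post randomisation will be withdrawn from treatment". One limb is a diagnosis; the other is a deadline. The next sentence gives both the same follow-up: "If participants are withdrawn for this reason they will continue to be followed up until their safety (30 days post randomisation) assessment". The section then says that baseline plasma from these participants will not be analysed for the trial. It is kept for future research if consent allows and otherwise destroyed at site.

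Further on, Section 7.8 has a general rule for anyone withdrawn from trial treatment: "Subsequent assessments of patient safety and an end of study outcome will be completed as planned". Section 9.4 likewise keeps participants in follow-up after study drug is discontinued unless they decline.

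Section 11.7 defines the analysis population by diagnosis alone. It states "We will seek outcomes for all randomised participants with confirmed aSAH regardless of protocol adherence and include them in analyses under the allocated group" and adds that "the analyses will be by intention to treat for all randomised participants whose confirmed diagnosis is aSAH". Its exclusion is worded by diagnosis too: "The anticipated 20% of randomised patients who are confirmed with alternative diagnoses will be excluded from all efficacy and mechanism analyses". Section 11.7.1 promises all reasonable efforts to obtain outcomes in confirmed aSAH and makes the primary analysis complete-case.

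**The concern.** A participant randomised with aneurysmal status unknown, whose aneurysm is confirmed on day 4, has confirmed aSAH and belongs to the Section 11.7 population. The same participant missed the 72-hour deadline, so the specific rule in Section 7.8 ends follow-up at day 30, about five months before the primary outcome is due. No sentence expressly restores the 6-month assessment once confirmation arrives.

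At stake is the primary outcome in members of the trial's own intention-to-treat population, lost through a protocol rule and not through a participant's choice or failure to make contact. With a complete-case primary analysis, such a participant simply drops out of it. Leaving the baseline sample unanalysed also removes the participant from the mechanism analysis, although Section 11.7 excludes only alternative diagnoses from that analysis. A 6-month mRS that is not sought in its window may not be recoverable.

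**Working it through.** **Step 1. Apply each section to one participant: status unknown at randomisation, aneurysm confirmed on day 4.**

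| Section | Consequence |
|---|---|
| 7.8, 72-hour rule | Follow-up to day 30 only; baseline sample not analysed |
| 7.8, general rule on withdrawal from treatment | 6-month outcome completed |
| 9.4 | Remains in follow-up unless declined |
| 11.7 | In the analysis population, under the allocated arm |
| 11.7.1 | All reasonable efforts to obtain the outcome |

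The list of circumstances attached to the general rule in 7.8 does not name an unconfirmed aneurysm. The specific day-30 sentence therefore governs on a literal reading, but a site could defensibly follow either.

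**Step 2. Can late confirmation occur?** Yes. Section 2.1.2 gives the usual timing only: "usually angiogram is performed within 48 hours or less of arrival at the neurosurgical centre". The notes to the schedule of assessments leave CT angiography to local practice, before or after randomisation. Aneurysm confirmation is recorded at day 3-5, a window that runs beyond 72 hours. Section 7.4 has a randomisation stratum for unknown status.

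**Step 3. Reproduce the plan's sample size.** Inputs from Section 11.1: common odds ratio 0.65, 90% power, 5% significance (taken as two-sided), 360 per group, 10% attrition, 800 confirmed aSAH, 1000 randomised. Allocation is 1:1 (Section 7.4). The Whitehead formula is

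N = 12(1.960 + 1.282)² / [(ln 0.65)² × (1 − Σp̄³)] = 679.5 / (1 − Σp̄³),

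where p̄ is the mean proportion of the two arms in each mRS category. The control mRS distribution is not printed. Four assumed seven-category distributions, each with 72% at mRS 0-2 and 9% deaths, give 358 to 364 per group, against 360 stated. Setting N = 720 implies 1 − Σp̄³ = 679.5/720 = 0.944. Then 720/0.90 = 800 and 800/0.80 = 1000. The plan's figures reproduce.

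**Step 4. Size of the loss.** The document gives no share of aSAH cases confirmed after 72 hours, so the share f is assumed. Late-confirmed cases are taken to lie within the 800 and to be lost in addition to the 10% attrition:

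N = 800 × (1 − f) × 0.90; power = Φ(√(N × 0.944/12) × 0.4308 − 1.960).

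| f (assumed) | Late-confirmed | N analysed | Power | Confirmed aSAH without 6-month mRS |
|---|---|---|---|---|
| 0% | 0 | 720 | 90.0% | 10.0% |
| 1% | 8 | 713 | 89.7% | 10.9% |
| 2% | 16 | 706 | 89.4% | 11.8% |
| 5% | 40 | 684 | 88.5% | 14.5% |
| 10% | 80 | 648 | 86.8% | 19.0% |

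**The case against.** The best reply is that the 72-hour limit simply defines when confirmation counts. Section 2.1.2 leaves participants without a confirmed aneurysm out of the outcome analysis. Section 7.8 excludes those who die before diagnosis. Section 11.7 speaks of exclusion for absence of confirmed aSAH. The unseen SAP might fix the timing. But none of these passages says that an aneurysm confirmed after 72 hours is not confirmed, and the 20% exclusion in Section 11.7 is worded as an alternative diagnosis. The reply shows that one reconciliation is possible, not that the protocol has made it. An SAP also cannot recover an outcome that was never collected.

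A second reply is that the general text in Sections 7.8 and 9.4 preserves follow-up, so nothing need be lost. This stands in part: loss is the literal result of the specific rule, not a certainty. It also confirms that the instructions conflict.

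A reader might go further and infer that late-imaged participants are sicker and that the treatment comparison is biased. The documents do not support this. Nothing links late confirmation to severity. Allocation is concealed and double-blind, and no route is evident by which treatment would change imaging time. Loss that is equal across arms alters whom the result describes; it does not by itself bias the comparison. Randomisation and analysis also account for WFNS grade and known aneurysmal status. Nor is there a serious power problem: at an assumed 5% the loss is under two points.

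**Conclusion.** The inconsistency holds and should be fixed. Section 7.8 ends follow-up by a deadline, Section 11.7 defines the population by diagnosis, and the general follow-up text does not clearly override the specific rule. Read literally, late-confirmed aSAH participants lose the primary outcome while remaining in the stated intention-to-treat population.

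The size is unknown and probably small, because angiography is usually early. Under the assumed 2-5% of 800 (16 to 40 participants), power is about 89.4-88.5% against 90%. These figures rest on the assumed share, on a two-sided test, and on a category term inferred from the plan's own 720. The sample size itself is sound. The case rests on avoidable loss of primary outcome data and on conflicting instructions to sites. It does not rest on between-arm bias, which is unlikely under blinding, or on power.

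**What to change.** Reconcile Sections 7.8, 9.4, 11.7 and 11.7.1:

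- Limit day-30-only follow-up to participants in whom aSAH is not confirmed.
- State that any participant whose aneurysm is confirmed after 72 hours, and before the 6-month assessment falls due, has that assessment and is analysed under the allocated arm, whether or not study drug was stopped.
- Retain that participant's baseline sample for the mechanism analysis, with no destruction at site while the diagnosis is open. The day 3-5 sample may still be absent, because Section 7.8 stops sampling on withdrawal from treatment; it would then be a missing value.

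The 72-hour treatment-stopping rule is outside this point. The cost is a protocol clarification, some sample handling, and probably a small number of extra 6-month assessments through the existing central telephone process.
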